4.2.3. Visit 3 (Month 4) +/- 4 days

Subjects will continue to take BLI400 daily and will return to the clinic for Visit 3 (Day 120). Vital signs (See section 4.1 for details) will be recorded. Study personnel will weigh returned bottles and count rescue bisacodyl for accountability purposes. Subjects will be queried for any adverse events or changes to their concomitant medications.

Subjects will complete the PAC-QOL and PAC-SYM questionnaires. Samples for chemistry, hematology and urinalysis will be repeated as outlined in Section 4.1. Subjects will be dispensed 2 new bottles of study medication. Subjects will be instructed to return all bottles and bisacodyl at the next follow up visit.

4.2.4. Visit 4 (Month 6) +/- 4 days

Subjects will continue to take BLI400 daily and will return to the clinic for Visit 4 (Day 180). Vital signs (See section 4.1 for details) will be recorded. Study personnel will review returned bottles and rescue bisacodyl for accountability purposes. Subjects will be queried for any adverse events or changes to their concomitant medications. Subjects will complete the PAC-QOL and PAC-SYM questionnaires. Samples for chemistry, hematology and urinalysis will be repeated as outlined in Section 4.1. Subjects will be dispensed 3 new bottles of study medication. Subjects will be instructed to return all bottles and bisacodyl at the next follow up visit.

4.2.5. Visit 5 (Month 9) +/- 4 days

Subjects will continue to take BLI400 daily and will return to the clinic for Visit 5 (Day 270). Vital signs (See section 4.1 for details) will be recorded. Study personnel will review returned bottles and rescue bisacodyl for accountability purposes. Subjects will be queried for any adverse events or changes to their concomitant medications. Subjects will complete the PAC-QOL and PAC-SYM questionnaires. Samples for chemistry, hematology and urinalysis will be repeated as outlined in Section 4.1. Three new bottles of study medication will be dispensed at this visit. Subjects will be instructed to return all bottles and bisacodyl at Visit 6.

4.2.6. Visit 6 (Month 12 or Early Term) +/- 4 days

Subjects will return at Day 360 for their final clinic visit. Vital signs (see section 4.1 for details) and ECGs will be recorded. A physical examination will be performed. Study personnel will weigh returned bottles and count bisacodyl for accountability purposes. Subjects will be queried for any adverse events or changes to their concomitant medications. Subjects will complete the PAC-QOL and PAC-SYM questionnaires. Samples for chemistry, hematology and urinalysis will be repeated as outlined in Section

4.1. Clinically significant laboratory abnormalities present at Visit 6 should be followed until resolved or are considered stable.

4.2.7. Follow-up Telephone Call (*Day 374*) +/- 4 days

At Day 374, approximately 2 weeks after the last study visit or early term visit, site personnel will contact subjects by telephone to query if any new adverse events have occurred and if any adverse events ongoing at Visit 6 have resolved. Subjects will also be asked about the status of their concomitant medications.

4.3. Tabulated Study Procedures

The following graphically depicts the flow of study procedures at each visit.

Procedures	Visit 1 Day 0	Visit 2 Month 2 +/- 4 days	Visit 3 Month 4 +/- 4 days	Visit 4 Month 6 +/- 4 days	Visit 5 Month 9 +/- 4 days	Visit 6 Month 12/ ET +/- 4 days	 Day 374 +/- 4 days
Informed Consent	X						
Inclusion/Exclusion Criteria Review	X						
Medical History	X						
Physical Examination	X					X	
Vital Signs ¹	X	X	X	X	X	X	
Electrocardiogram	X	X				X	
Review of Concomitant Medication	X	X	X	X	X	X	X
Urine Pregnancy Test (if applicable) ²	X						
Enroll Eligible Subjects	X						
Subject to Complete PAC-QOL, PAC-SYM	X	X	X	X	X	X	
Blood Sample for Chemistry Testing	X	X	X	X	X	X	
Blood Sample for Hematology Testing	X	X	X	X	X	X	
Urine Sample for Urinalysis	X	X	X	X	X	X	
Blood Sample for Serum Pregnancy Testing				X		X	
Dispense Study Drug and Rescue Bisacodyl	X	X	X	X	X		
Study Drug and Rescue Bisacodyl Accountability		X	X	X	X	X	
Assess Safety		X	X	X	X	X	X

¹blood pressure and pulse while seated and after standing for 2 minutes, temperature, weight and height (@Visit 1 only)

²refer to Section 4.4

4.4. Pregnancy

Subjects who are female and of childbearing potential must have a urine pregnancy test done at screening. A positive result will rule out the participation of the subject in the study. Serum pregnancy tests will be performed at Visits 4 (Month 6) and 6 (Month 12). If a subject becomes pregnant during the study, the subject must be removed from the study and followed until one month after the end of the pregnancy.

Female study subjects must be surgically sterilized or using oral contraceptives, depot contraceptives, double-barrier method, intrauterine device, or testifies that she is monogamous with a vasectomized partner. Subjects practicing abstinence must agree to use an acceptable form of birth control should they become sexually active during the study.

Women with a history of bilateral tubal ligation are not considered of childbearing potential and are not required to have a urine pregnancy test at screening.

Oral contraceptives, hormone implants, and injections are only considered effective if started at least 1 month before the study.

Menopausal status is defined when menses have been absent for 12 months in a woman of appropriate age (usually 45 to 55 years) who has no other suspected or identified cause of amenorrhea.

4.5. Concomitant Medications

The use of concomitant medication will be recorded from 7 days prior to Visit 1 until the end of the study at the telephone contact on Day 374. Subjects enrolled in this study will not be permitted to take any laxatives (other than the sponsor supplied rescue bisacodyl), whether prescription or over-the-counter, from Visit 1 until after completion of Visit 6. Any restricted laxative use during the study may result in termination of subject's participation. Subjects may not initiate treatment with any constipating medication.

5. ADVERSE EVENTS

5.1. Adverse Event Definition and Reporting

An Adverse Event (AE) is any untoward medical occurrence associated with the use of a drug in humans, whether or not considered drug related. An AE can therefore be any unfavorable and unintended sign (including a clinically significant abnormal laboratory finding), symptom, or disease temporally associated with the use of a medicinal (investigational) product.

Adverse event collection will coincide with the subject providing informed consent to participate in the study and will conclude with the end of study participation at Day 374 Follow-up Call. Diarrhea should be reported as an adverse event if a subject has more than 3 watery stools per day. Subjects with clinically significant laboratory results at Visit 6 which are classified by the Investigator as adverse events should return for a repeat blood draw. Subjects will be instructed to report promptly adverse events to the Investigator. The Investigator will record date/time of report, date/time of onset, description of the adverse event, severity of adverse event, action(s) taken regarding treatment of the event, action(s) taken regarding study participation, duration of adverse event, and the Investigator's assessment of relationship of adverse event to study treatment.

The Investigator should assess the severity of each adverse event using the following categories:

Grade	Severity	Description
1	Mild	Barely noticeable, does not influence functioning Causing no limitations of usual activities
2	Moderate	Makes participant uncomfortable, influences functioning Causing some limitations of usual activities
3	Severe	Severe discomfort, treatment needed Severe and undesirable, causing inability to carry out usual activities
4	Life threatening	Immediate risk of death Life threatening or disabling
5	Fatal	Causes death of the participant

The Investigator should assess the relationship to study drug for each adverse event using the following categories:

Categories of Attribution:	Description
UNRELATED	There is no evidence of any causal relationship.
POSSIBLE	There is some evidence to suggest a causal relationship (e.g., the event occurred within a reasonable time after administration of the trial medication). However, the influence of other factors may have contributed to the event (e.g., the patient's clinical condition, other concomitant events).
PROBABLE	There is evidence to suggest a causal relationship, and the influence of other factors is unlikely .
DEFINITE	There is clear evidence to suggest a causal relationship, and other possible contributing factors can be ruled out .

In published Phase 3 studies, adverse events associated with BLI400 administered at doses required for effective treatment of constipation included flatulence, nausea, vomiting, abdominal cramping or pain and bloating. These adverse reactions were transient and subsided rapidly upon dose adjustment or cessation.

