9. DATA ANALYSIS

9.1. Sample Size

Consistent with *ICH E1A Guideline for Industry, the Extent of Population Exposure to Assess Clinical Safety: for Drugs Intended for Long-term Treatment of Non-Life-Threatening Conditions (March 1995)*, 300 subjects will be treated with BLI400 for 12 months. This will allow for detection of adverse events that may increase in frequency or severity over time.

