9.2. Parameters to be Analyzed

The primary objective of this study is to investigate the safety of BLI400 used chronically for 12 months in subjects with constipation. Safety will be analyzed using ECG, vital signs, chemistry, hematology and urinalysis and adverse event data. Treatment emergent adverse event rates will be descriptively presented by preferred term, severity, and relationship to treatment.

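### The AE severity scale in 5.1 has no magnitude criteria, so an asymptomatic laboratory AE that is not life-threatening cannot be Moderate and has only an unclear route to Severe

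*Combined protocol and SAP*

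**What the plan says.** The AE definition in Section 5.1 covers "any unfavorable and unintended sign (including a clinically significant abnormal laboratory finding), symptom, or disease". Laboratory findings are named. ECG and vital-sign findings are not, and would enter through the general term *sign*.

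The same section then sets one scale for all AEs: "The Investigator should assess the severity of each adverse event using the following categories". The lower three grades are worded as follows:

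- Grade 1, Mild: "Barely noticeable, does not influence functioning Causing no limitations of usual activities"
- Grade 2, Moderate: "Makes participant uncomfortable, influences functioning Causing some limitations of usual activities"
- Grade 3, Severe: "Severe discomfort, treatment needed Severe and undesirable, causing inability to carry out usual activities"

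Grade 4 covers immediate risk of death and life-threatening or disabling events, and Grade 5 is death. The file carries the protocol text twice, and both copies have the same table. Neither gives a separate grading rule for laboratory, vital-sign or ECG findings.

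Section 9.2 uses the grade directly: "Treatment emergent adverse event rates will be descriptively presented by preferred term, severity, and relationship to treatment". Section 9.1 justifies the study size by saying: "This will allow for detection of adverse events that may increase in frequency or severity over time".

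**The concern.** The scale measures what the subject feels and can do. A raised creatinine or a low potassium often causes neither discomfort nor loss of function, and the scale has no other way to separate a small abnormality from a large one at the lower grades.

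This matters because the summary sheet names AEs, ECG data and laboratory comparisons as the primary endpoint. The introduction also gives reasons to look closely at chemistry. Animal studies showed electrolyte changes and occasional renal tubular degeneration, and one human study showed a rise in potassium within the normal range. The design has one open-label arm, so no control group would reveal or offset uneven grading. A reader of the severity table would take the Mild count for laboratory AEs at face value, although part of it reflects only the absence of symptoms.

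**Working it through.** No arithmetic applies. The plan gives no figure tied to the scale, and the question is one of wording. Take a laboratory AE with no symptoms and no loss of function, and test it against each grade in 5.1.

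| Grade | What the wording requires | Open to this AE? |
|---|---|---|
| 1 Mild | Barely perceptible, no effect on function or activities | Yes |
| 2 Moderate | Discomfort and some effect on function or activities | No |
| 3 Severe | Severe discomfort and a need for treatment; inability to carry on usual activities | Only if the need for treatment is enough alone; the text does not say |
| 4 Life threatening | Immediate risk of death; life-threatening or disabling | Yes, if the value carries that risk; no symptom is required |
| 5 Fatal | Death | Yes, if fatal |

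This gives three non-fatal cases:

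1. **Untreated, no immediate risk of death.** Only Grade 1 fits. Two such AEs with very different values get the same grade, and one that worsens within this range keeps its grade.
2. **Treated, no immediate risk of death.** If treatment must accompany severe discomfort, the grade is 1. If treatment is enough alone, the grade is 3. Two sites can record the same value two grades apart, and both would be following the text.
3. **Immediate risk of death.** Grade 4 fits.

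The scale therefore has a gap at Grade 2 and an ambiguity at Grade 3 for this class of event.

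Next, check what else in the plan shows magnitude:

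- **Laboratory (9.3.2):** mean, minimum, maximum and SD by visit, change from baseline, shift tables, and a listing of subjects with clinically significant values. No shift categories are stated, so it is not known whether the shift tables separate degrees of abnormality.
- **Vital signs (9.3.2):** by-visit summaries and shift tables.
- **ECG (end of 9.3.2):** descriptive statistics, including minimum and maximum, and ANOVA across Visits 1, 2 and 6. No shift table, threshold categories or listing of abnormal values is stated.
- **SAEs (Section 6):** an event needing intervention to prevent permanent damage is serious whatever its grade.

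None of these feeds back into the grade tabulated under 9.2.

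**The case against.** The strongest reply is that laboratory magnitude does not depend on the AE grade. The summary sheet lists the comparison of laboratory values separately from AE data, and 9.3.2 plans several direct displays of them. Seriousness is judged separately as well. Severity is left to the investigator, and a laboratory result becomes an AE only after a judgement of clinical significance. On this view numeric grading is an enhancement that the protocol never promised.

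Much of that stands. It confines the point to one descriptive table. It does not remove the point, because the stated rule still grades this class of AE without regard to size in a table that reports primary safety data. Seriousness and severity are also different attributes, so an SAE flag leaves the grade unchanged.

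A reader might go further and draw three inferences that the documents do not support:

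- **Every asymptomatic laboratory AE is Mild, however extreme.** Grade 4 needs no symptoms, and Grade 3 may be open to a treated case. The most extreme values are the likeliest to reach those grades.
- **The study cannot show worsening over time.** By-visit summaries, changes from baseline and shift tables can show it for laboratory values. In addition, 9.3.2 compares only AE rates between study periods. No analysis of severity by period is planned for any AE, so the scale is not what prevents one.
- **ECG AEs are covered in the same explicit way as laboratory AEs.** Only laboratory findings are named in 5.1.

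**Conclusion.** The point holds in a limited form. For an AE that is an asymptomatic laboratory finding without immediate risk of death, the 5.1 scale has no usable Moderate grade and an undefined entry to Severe. Untreated cases are tabulated as Mild whatever their size, and treated cases can differ by two grades between sites. The same follows for ECG and vital-sign AEs if they are recorded as signs.

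The reach is one descriptive tabulation in 9.2. The laboratory analyses in 9.3.2 and the SAE reporting do not depend on it. The number of subjects affected cannot be given: the documents state no rate of laboratory AEs, no share that is asymptomatic and no share that is treated. The conclusion rests only on investigators applying the 5.1 wording as written. It is a modest improvement worth making because it is cheap, and it does not put the study's safety assessment as a whole in doubt.

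**What to change.** - In 5.1, keep the functional scale for symptomatic events.
- For AEs that are laboratory, vital-sign or ECG findings, derive the severity grade from the recorded value. Use a published or sponsor-defined numeric grading table fixed before enrolment, and state which value counts when an event spans several measurements.
- Use that derived grade in the 9.2 severity table.
- State whether the need for treatment alone meets Grade 3.
- State that ECG and vital-sign findings can be AEs, if that is intended.

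The cost is one grading table and a short derivation program. Scheduled laboratory samples go to a central laboratory, vital signs are recorded at every clinic visit, and ECG data are entered in the eCRF, so scheduled values need no new collection. The downside is that some AEs now called Mild will move to a higher grade, which the report should explain.

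This change corrects the grade. It does not add an analysis of severity over time; if the sponsor wants one to support the statement in 9.1, it has to be specified separately.

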6. SERIOUS ADVERSE EVENTS REPORTING

A Serious Adverse Event (SAE) is any untoward medical occurrence that results in at least one of the following outcomes:

- Results in death
- Is life-threatening
- Requires inpatient hospitalization or prolongation of existing hospitalization
- A persistent or significant incapacity or substantial disruption of the ability to conduct normal life functions
- Is a congenital anomaly/birth defect
- Requires medical or surgical intervention to prevent permanent impairment or damage

SAE collection will coincide with the subject providing informed consent to participate in the study and will conclude 30 days after a subject's last dose of study medication. Should a serious and/or unexpected adverse event occur, the Investigator must notify Braintree Laboratories immediately. The Investigator will make a decision regarding continuing the subject's study participation, and may request input from Braintree Laboratories. The Investigator will be responsible for recommending or providing the subject with appropriate medical therapy. All subjects experiencing serious adverse events will be followed until satisfactory resolution occurs. Braintree Laboratories must be kept apprised of all follow-ups relative to serious adverse events. In addition, Investigators must comply with the SAE reporting requirements of the Institutional Review Board with oversight of the study.

Any serious and/or unexpected adverse events that occur during the study will be reported to Braintree Laboratories as follows:

Contact Telephone Numbers:

During Business hours
(M-F, 8:30 am – 5:00 pm EDT)
After hours or weekends

Braintree Laboratories and its medical monitor will review the report and determine whether an FDA Form 3500A will also be completed and sent to FDA.

7. INSTITUTIONAL REVIEW BOARD AND INFORMED CONSENT

Institutional Review Board (IRB) review and approval of the study protocol and Informed Consent Form will be obtained prior to initiation of the study. Amendments to the study protocol and consent form generated during the course of the study will also require IRB approval.

8. MANAGEMENT OF INTERCURRENT EVENTS

8.1. Modification of Protocol

Neither an Investigator nor Braintree Laboratories will modify the protocol without first obtaining the concurrence of the other and the IRB. Investigators that continually violate the protocol or commit a serious violation may be subject to termination from the study. The study may be halted if at any time an Investigator or Braintree Laboratories deems the incidence or severity of adverse events to be unacceptable.

8.2. Subjects Discontinued from the Study

Subjects may be dropped from the study for any of the following reasons:

- 1) Subject took prohibited medications during the Treatment Period
- 2) An adverse event requiring discontinuation (including failure to tolerate study medication).
- 3) The Investigator decides that the subject should be dropped from the study (e.g. serious adverse event, protocol violation, non-compliance).
- 4) The subject decides to withdraw from the study. Subjects are free to withdraw their consent and discontinue participation in the study at any time.

Braintree Laboratories should be contacted if possible prior to discontinuation of any subject. If a subject is discontinued from the study, Braintree Laboratories must be notified with an explanation for all discontinuances.

9. DATA ANALYSIS

9.1. Sample Size

Consistent with *ICH E1A Guideline for Industry, the Extent of Population Exposure to Assess Clinical Safety: for Drugs Intended for Long-term Treatment of Non-Life-Threatening Conditions (March 1995)*, 300 subjects will be treated with BLI400 for 12 months. This will allow for detection of adverse events that may increase in frequency or severity over time.

9.2. Parameters to be Analyzed

The primary objective of this study is to investigate the safety of BLI400 used chronically for 12 months in subjects with constipation. Safety will be analyzed using ECG, vital signs, chemistry, hematology and urinalysis and adverse event data. Treatment emergent adverse event rates will be descriptively presented by preferred term, severity, and relationship to treatment.

9.3. Planned Analyses

9.3.1. Demographic and Baseline Characteristics

Baseline demographic characteristics will be tabulated with N, mean, standard deviation, and range of values where appropriate

- Age
- Gender
- Race/ethnicity
- Constipation History

9.3.2. Safety Analyses

Analysis of safety will be performed using the modified Intent to Treat population (see Section 9.4).

Adverse Events

Adverse Events will be coded using the MedDRA classification to provide a preferred term and primary system organ class for each event. Proportions of subjects with adverse events will be presented for the overall study population, and each demographic subgroup (age, gender and race). Tables of AEs will be presented by system organ class and preferred term, and include overall totals for AEs within each system organ class. Counting will be done by subject and not by event. A table of counts and percentages will also be made of those subjects with SAEs or AEs which led to withdrawal from the study.

Treatment-emergent AEs are defined as adverse events that had an onset day and time on or after the day and time of the first dose of study drug until the Day 374 Follow-up Call. Adverse Events having missing onset dates will be considered as treatment emergent.

The difference in adverse event rates between study periods will be tested by Chi-Square or Fisher's exact test with 95% confidence intervals.

Laboratory Parameters

Summary statistics (i.e., mean, minimum, maximum, standard deviation, and number of subjects) will be presented for each laboratory parameter at each visit. Laboratory data will be summarized for the overall population and the elderly and non-elderly subgroups. When calculating the summary statistics only, the last observation within a visit window will be used if there are multiple observations. Changes from baseline (Visit 1) will be presented in a similar format. An additional listing will be provided of those subjects who have clinically significant laboratory values. The data will also be presented as shift tables and clinically significant abnormalities will be examined.

Results of laboratory tests for the change from baseline (Visit 1) and group differences will be tested using ANOVA.

Vital Signs

Summary statistics (i.e., mean, minimum, maximum, standard deviation, and number of subjects) will be presented for each vital sign at each visit and compared to the values obtained at Visit 1. When calculating the summary statistics only, the last observation within a visit window will be used if there are multiple observations. The data will also be presented as shift tables and clinically significant abnormalities will be examined.

ECG variables will be tabulated and presented for data collected at each visit. Data will be tabulated and summarized with descriptive statistics (N, mean, SD, CV%, SEM, minimum, and maximum) for each of the ECG variables. The differences in ECG variables between Visit 1 (Baseline), Visit 2 and Visit 6 will be tested using ANOVA.

